3. The End-of-Treatment (EOT) visit should be performed as soon as feasible following the decision to discontinue study drug dosing and prior to initiation of alternate therapies. This visit may be combined with the 30-day post-treatment follow-up visit, if the windows overlap, with required assessments completed once for the combined visit.
4. Follow-up visit should occur 30 (± 3) days after the last dose of CDX-3379. Thereafter, patients should be contacted (may be via telephone) every 12 (± 2) weeks until study closure for survival status and subsequent therapies. For patients who have discontinued study therapy for reasons other than progression, imaging studies to assess response should be obtained every 12 (± 2) weeks (relative to last disease assessment) until disease progression or until patients are started on subsequent therapy, whichever occurs sooner. For these patients, the first survival status may be scheduled to coincide with the first post-treatment disease assessment, rather than relative to the 30-day follow-up.
5. Medical history includes prior/concurrent conditions and cancer history including cancer mutation status and HPV status, prior treatments and surgical history. At Day 1, medical history is updated prior to administration of study drug.
6. Unless prior agreement is reached with the Medical Monitor for submission of archival tumor, biopsy is to be performed of an accessible site (primary or metastatic) that can be biopsied with acceptable clinical risk (as judged by the investigator), obtaining a minimum of 3-5 core biopsies for biomarker analysis. FNAs are not acceptable. The biopsy site chosen should not have been previously irradiated and must be distinct from RECIST 1.1 target lesions, unless the biopsy is obtained prior to the screening disease assessment.
7. Pregnancy tests are required only for women of childbearing potential (excluding patients who are post-menopausal with absence of menses for at least 1 year and/or surgically sterilized). A serum pregnancy test must be performed during Screening. If the serum pregnancy test is performed more than 7 days prior to Day 1, then a urine or serum pregnancy test must also be performed on Day 1 with results reviewed prior to dosing.

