18. See Section 10.2.1 and [Appendix 2](#). Disease evaluation done at screening, near the end of every 2nd cycle (i.e., after day 15 of cycles 2, 4, 6, 8, etc. and prior to dosing for the next cycle), and, for patients who have not experienced progression at end of treatment, every 12 (\pm 2) weeks until progression or initiation of alternate cancer therapies. Disease evaluation is required at end of treatment only if disease progression is not previously documented. If a partial or complete response is noted, a follow-up radiographic assessment must be done no sooner than 28 days later to confirm response. Prior to any intervention (such as surgical resection, palliative radiation or alternate anticancer therapy), every effort should be made to perform a tumor response assessment in order to document progression and/or confirm an objective response.
19. Unless otherwise specified, all study assessments should be performed prior to administration of study treatment and may be performed up to 24 hours prior to treatment administration if assessments remain within the specified visit window. CDX-3379 should be administered first, with a 1-hour observation period before administration of cetuximab. Diarrhea prophylaxis is required in accordance with Section 8.4.1.4
20. Cetuximab will be administered weekly on Days 1, 8, and 15 of each cycle. On Day 1 of each Cycle, cetuximab should be administered approximately 1 hour after the completion of CDX-3379 administration and after collection of the 60 minute post-infusion PK blood sample. As a routine precaution, patients should be observed for at least 1 hour after the end of the cetuximab infusion. See Section 8.4.2 for guidance on cetuximab premedication and diarrhea prophylaxis. See Section 8 for additional details regarding study treatment dosing, precautions, monitoring, and management of toxicity.
21. All concomitant medications will be documented if taken within 28 days prior to Day 1, and either (whichever occurs sooner): a) through the 30-day post-treatment follow-up, or b) initiation of alternate anticancer therapy. In addition, all anticancer surgeries or medications and response to those medications, as well as any concomitant medications required to treat study drug-related serious adverse events (SAEs), should also be recorded throughout the duration of study follow-up. See Section 9 for further guidance.

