7 INVESTIGATIONAL PLAN

7.1 Overall Design and Plan of the Study

This is an open-label, multicenter Phase 2 study of CDX-3379 in combination with cetuximab in patients with cetuximab-resistant HNSCC. Patients will be treated with CDX-3379 plus cetuximab until progressive disease, unacceptable toxicity, or other criteria for discontinuation of study treatment (Section 7.4.1) are met.

The study was initially designed according to a Simon's 2-stage design in which one tumor response (CR or PR) would need to be observed in the first 13 evaluable patients before completion of accrual to a total of 27 evaluable patients. Patients who discontinue treatment in the absence of progression/symptomatic deterioration/death before the first tumor assessment will be considered unevaluable for primary analysis and will be replaced. Following completion of stage 1 of the study, where 1 complete response was observed, emerging biomarker data were reviewed to assess correlation with efficacy. In the overall CDX-3379 development program, in a small patient dataset, FAT1 and NOTCH1, NOTCH2 and NOTCH3 mutations appeared to be associated with clinical activity including objective response and durable stable disease. Given these findings, the study design has been amended to enroll up to approximately 45 total patients, including at least 15 patients whose tumor harbor a FAT1 mutation based on retrospective gene sequencing. Screening tissue samples will be required to be submitted as directed by the Sponsor at the time of enrollment to allow for gene sequencing and tracking the number of patients whose tumor harbor a FAT1 mutation.

Tumor assessments will be performed approximately every 6 weeks during treatment. Patients who discontinue treatment in the absence of progression will continue to have assessments approximately every 12 weeks until documented progression or initiation of alternate anticancer therapies. Tumor response will be assessed by the investigator in accordance with RECIST 1.1 guidelines (Eisenhauer, et al. 2009) (Section 10.2.1 and Appendix 2).

Continuous evaluation of toxicity will be performed by the investigators and Celldex throughout the entire course of patient treatment and through 30 days following the last dose of CDX-3379. Subsequently, patients will be followed for survival, with contact every 12 weeks until study closure.

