 - c. Platelet count \geq 100,000/mm³
 - d. Aspartate aminotransferase (AST) and alanine aminotransferase (ALT) \leq 2.5 \times upper limit of normal (ULN) (\leq 5 \times ULN for cases involving liver metastasis)
 - e. Bilirubin \leq 1.5 \times ULN (\leq 5 \times ULN for cases of documented or suspected Gilbert's disease)

- f. Serum creatinine \leq 1.5 g/dL or calculated creatinine clearance (CrCl) \geq 60 mL/min for patients with serum creatinine $>$ 1.5 x ULN
- g. Serum magnesium \leq 1.5 \times ULN
- h. Serum calcium and potassium within normal limits

10. Life expectancy \geq 12 weeks

11. Eastern Cooperative Oncology Group (ECOG) Performance Status of 0 or 1 ([Appendix 3](#))

12. Both male and female patients enrolled in this trial must agree to use highly effective contraception during the course of the trial and for at least for 6 months after the final dose of CDX-3379 or cetuximab, whichever is later. Patients and/or partners who are surgically sterile or postmenopausal are exempt from this requirement.

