9 CONCOMITANT THERAPY

Please refer to the study entry criteria for the required “wash-out” period for specific therapies, relative to start of study treatment.

Required prophylactic medications are described in Section 8.4.

Patients may continue to use any ongoing medications not prohibited by the inclusion/exclusion criteria. However, efforts should be made to maintain stable doses of concomitant medications during the course of study treatment. Patients must be instructed not to take any medications, including over-the-counter products, without first consulting with the investigator.

Investigators may prescribe concomitant medications or treatments deemed necessary to provide adequate supportive care, such as those outlined in Section 8.3.1, Section 8.4.1.4. and 8.4.2.

However, while on study, when clinically appropriate, patients should strictly follow the study-prescribed treatment regimen. The following are prohibited throughout the treatment period:

- Concurrent administration of any anticancer therapies (including chemotherapy, radiotherapy, immunotherapy, biologic or hormonal therapy) and/or other investigational agents (Note: concurrent use of hormones for conditions unrelated to cancer [e.g., insulin for diabetes and hormone replacement therapy] is acceptable.)
 - Following treatment, patients may receive any appropriate alternate therapies.

The Medical Monitor must be notified if a patient receives any prohibited medication during the treatment period.

All concomitant medication will be documented in the patient's medical record and CRF if taken within 28 days prior to randomization/enrollment, and either (whichever occurs sooner): a) 28 days after last dose of study treatment (either CDX-3379 or cetuximab), or b) initiation of alternate anticancer therapy. All anticancer medications taken throughout the study (including follow-up) should also be recorded, as should concomitant medications required to treat study drug-related serious adverse events (SAEs).

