- Progression of neoplasia should not be reported as an AE or SAE. Findings that are clearly consistent with the expected progression of the underlying cancer should not be reported as an AE, and hospitalizations due to the progression of cancer do not necessarily qualify for an SAE. If there is any uncertainty about a finding or event being due solely to progression of neoplasia, the finding or event should be reported as an AE or SAE as appropriate.
- Death due to disease progression occurring within 28 days of study treatment should be reported to Celldex within 24 hours of the site’s awareness of the event; however, these events should not be documented as AEs or SAEs. If there is any uncertainty about the cause of death, the event should be reported as an SAE.
- Withdrawal due to an AE should be distinguished from withdrawal due to insufficient response, and recorded on the appropriate AE CRF page. For example, if an AE due to recurrence/progression of disease necessitates discontinuation from the study, the primary reason for study discontinuation should be recorded as “Progression of Disease” (not AE).

■ [REDACTED]

- Diagnostic and therapeutic non-invasive and invasive procedures, such as surgery, should not be reported as AEs. However, the medical condition for which the procedure was performed should be reported if it meets the definition of an AE. For example, an acute appendicitis that begins during the AE reporting period should be reported as the AE, and the resulting appendectomy should be recorded as treatment of the AE.

- Any AEs/SAEs resulting in death should be recorded with an end date equal to the death date, while other events ongoing at the time of death should be recorded with an outcome of "ongoing". If requested, a summary of available autopsy findings should be submitted as soon as possible to Celldex.

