10.2.5.3 Adverse Event/Serious Adverse Event Reporting

The investigator is to report all directly observed AEs and all AEs spontaneously reported by the study patient. In addition, each study patient will be questioned about AEs.

Adverse events and SAEs should be recorded on the CRF from the time the patient has received at least one dose of study treatment through (whichever occurs first) either a) the 30-day post-treatment follow-up visit, or b) initiation of alternate anticancer therapy.

However;

- Any SAE occurring any time after the reporting period must be promptly reported if a causal relationship to study treatment is suspected.
- For AEs or SAEs with a causal relationship to the investigational product, follow-up by the investigator is required until the event or its sequelae resolve to \leq grade 1, or stabilize for at least three months after the last administration of study treatment (whichever is sooner).

All AEs will be reported on the AE page(s) of the CRF, while SAEs will also be reported in an expedited fashion using the SAE report. The AE CRFs and SAE reports must be completed in a consistent manner; for example, the same AE term, causality, severity, and onset/resolution dates should be used on both forms.

In case of an SAE (regardless of causality), an SAE report must be completed and submitted to Celldex within 24 hours of the site's notification of the event, irrespective of the extent of available AE information. This timeframe also applies to additional new information (follow-up) on previously forwarded SAE reports. The investigator is obligated to pursue additional information required for thorough evaluation of each SAE as may be requested by Celldex.

Serious adverse event reporting to regulatory authorities and all participating investigators will be conducted by Celldex in accordance with 21 Code of Federal Regulations (CFR) 312.32 and international regulations, as appropriate.

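### AE collection ends 30 days after the last CDX-3379 dose, so a patient given Day 15 cetuximab has only about 16 days of collection after it, and the protocol and SAP disagree on the window

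*Protocol*

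**What the plan says.** **End of AE collection.** Protocol 10.2.5.3 records AEs and SAEs on the CRF from the first dose until the first of two events: "either a) the 30-day post-treatment follow-up visit, or b) initiation of alternate anticancer therapy". Table 1 note 22 agrees.

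**Date of that visit.** Table 1 note 4 says: "Follow-up visit should occur 30 (± 3) days after the last dose of CDX-3379". Protocol 10.1.3 and SAP Exhibit 4 note 3 repeat this. Protocol 7.1 and SAP 2.1 likewise run toxicity evaluation "through 30 days following the last dose of CDX-3379".

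**The two drugs.** Protocol 10.2.5.1 treats both CDX-3379 and cetuximab as study treatment for AE purposes. SAP 2.3 gives CDX-3379 on Day 1 of each 21-day cycle and cetuximab on Days 1, 8 and 15. Table 1 note 18 places scheduled scans "after day 15 of cycles 2, 4, 6, 8, etc. and prior to dosing for the next cycle".

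**Concomitant medications.** Protocol Section 9 collects them until "28 days after last dose of study treatment (either CDX-3379 or cetuximab" or new anticancer therapy, whichever is sooner. Table 1 note 21 and SAP Exhibit 4 note 21 end collection at the 30-day follow-up instead, with the same exception for new therapy.

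**After the reporting period.** Protocol 10.2.5.3 keeps SAEs suspected to be related to study treatment reportable at any time. It adds: "For AEs or SAEs with a causal relationship to the investigational product, follow-up by the investigator is required", until resolution or stabilisation.

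**SAP tables.** SAP 7.2 plans separate displays of CDX-3379-related and cetuximab-related AEs. It presents events up to 30 days after the last dose date and does not say of which drug.

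**The concern.** Safety of the combination is a secondary objective, and cetuximab-related AEs have their own planned table. The clock that ends collection nevertheless starts at the last dose of only one of the two drugs, the one given least often. Under the normal schedule a patient can receive two more cetuximab doses after the last CDX-3379 dose, and observation after the final cetuximab dose shortens accordingly.

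Two things are at stake. First, ascertainment after cetuximab is shorter than the 30 days a reader would assume, and it is uneven between patients because it depends on the cycle day of the last cetuximab dose. Second, the documents give more than one answer on when collection and tabulation end, so sites and programmers could apply different windows.

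**Working it through.** The plan gives no figure for days of AE collection after the last cetuximab dose, so there is none to reproduce. The check is calendar arithmetic within the final cycle.

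**Inputs**
- Last CDX-3379 dose: Day 1 (SAP 2.3).
- Last cetuximab dose: Day C, where C = 1, 8 or 15 (SAP 2.3; Table 1 note 20).
- Visit that ends AE recording: 30 ± 3 days after CDX-3379 (Table 1 note 4).
- Section 9 medication window: 28 days after the last dose of either drug, read as the later of the two.

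**Formulas**
- Visit day V = 1 + 30 = Day 31, range Day 28 to Day 34.
- AE collection after the last cetuximab dose = V − C.
- Section 9 end = C + 28.
- Overrun of Section 9 past the visit = (C + 28) − V.

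| Last cetuximab | AE collection after it, days (range) | Section 9 end | Overrun past the visit, days (range) |
|---|---|---|---|
| Day 15 | 31 − 15 = 16 (13 to 19) | Day 43 | 43 − 31 = 12 (9 to 15) |
| Day 8 | 31 − 8 = 23 (20 to 26) | Day 36 | 36 − 31 = 5 (2 to 8) |
| Day 1 | 31 − 1 = 30 (27 to 33) | Day 29 | 29 − 31 = −2 (−5 to 1) |

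If the Day 15 dose itself moves by ±1 day, the 13-to-19-day range widens to 12 to 20 days.

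**Which row applies.** Scheduled scans come after Day 15 of an even cycle and before the next dose. A patient who stops because of such a scan, and who received the Day 15 cetuximab, is in the first row.

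**SAP 7.2 window.** If the last dose date means CDX-3379, AE tables close on Day 1 + 30 = Day 31. If it means cetuximab on Day 15, they close on Day 15 + 30 = Day 45. The readings differ by 45 − 31 = 14 days, and under the second the table window extends 14 days beyond nominal collection.

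**Schedules side by side.** In Protocol Table 1, AE monitoring and medication review appear to end at the 30-day visit. In SAP Exhibit 4, as the text was extracted, both rows carry a further mark in the survival follow-up column, yet Exhibit 4 notes 21 and 22 still end routine documentation at the 30-day follow-up.

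**The case against.** **The CDX-3379 anchor is deliberate and consistent.** The visit is tied to CDX-3379 throughout, and the study schema treats stopping CDX-3379 as stopping study treatment. This stands as a description. It does not explain why AE collection for a two-drug regimen should ignore the later drug, and the available text gives no rationale. It also does not settle the medication, Exhibit 4 or SAP 7.2 discrepancies.

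**A reader might infer that late cetuximab events are never recorded.** The documents do not support that. Suspected-related SAEs stay reportable without time limit, survival contacts continue every 12 weeks, and SAP Exhibit 4 may indicate AE review at those contacts. That mark could reflect only the open-ended SAE rule in note 22. What is exposed is new non-serious AEs and SAEs not suspected to be related.

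**A reader might infer that every patient stopping at a scan is affected, or that only a shared Day 1 last dose avoids the gap.** Neither holds. The Day 15 dose may have been delayed or omitted, cetuximab may have stopped before CDX-3379, and new therapy may close collection earlier in any case. The share of patients affected is not stated.

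**A reader might cite other windows as further gaps.** Contraception runs to "6 months after the final dose of CDX-3379 or cetuximab, whichever is later", and there is a rule that "Death due to disease progression occurring within 28 days of study treatment should be reported to Celldex". The first outlasts any 30-day visit whatever the anchor. The second concerns deaths that are expressly not AEs and does not depend on the visit. Neither shows a collection gap.

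**A reader might infer that cetuximab-only events have no follow-up duty.** The synopsis lists CDX-3379 as the investigational treatment and cetuximab as additional therapy, which favours that reading. But the term investigational product is not defined in the visible text, and the same sentence runs its clock from the last study treatment, which covers both drugs. The wording is unclear, not a demonstrated omission.

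**No bias has been measured.** This is correct. Only its direction can be stated.

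**Conclusion.** The point holds as a shortened and uneven collection window combined with conflicting definitions of where it ends. For a patient whose last CDX-3379 was on Day 1 and last cetuximab on Day 15 of the final cycle, AE collection covers 16 days (13 to 19) after cetuximab; with a last dose on Day 8 it covers 23 days. This assumes that dosing followed the schedule, that treatment ended at a scheduled scan, and that new anticancer therapy did not start before the visit.

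Compared with a full 30 days after the later drug, the shorter window can only lower the reported cetuximab-related and combination AE rates. The documents give no late-onset event rate and no distribution of the last cetuximab day, so the size of the effect cannot be derived, and the plan's own exceptions limit it.

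The conflict over concomitant medications does not depend on any event rate: on the later-dose reading, Section 9 runs to Day 43, about 12 days (9 to 15) past the visit at which Table 1 note 21 ends collection. Counted from CDX-3379 alone, Section 9 would end on Day 29, before the nominal visit. The two texts would still differ, but the overrun would disappear.

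This should be corrected. It does not call the primary response analysis into question.

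**What to change.** Define one window for AE/SAE and concomitant-medication collection: to 30 days after the last dose of CDX-3379 or cetuximab, whichever is later, or to the start of new anticancer therapy if that is sooner.

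- Apply it in Protocol Table 1 notes 4, 21 and 22 and Protocol 7.1, 9, 10.1.3 and 10.2.5.3.
- Apply it in SAP 2.1 and in SAP Exhibit 4, making the marks and notes agree on what is reviewed at survival follow-up.
- In SAP 7.2, state that the last dose date is the later of the two drugs' last doses, so that tabulation matches collection.
- Keep the existing visit at 30 days after CDX-3379 for PK and ADA sampling, and collect the remaining days by one telephone contact. After a Day 15 cetuximab dose, that contact falls at about Day 45, 14 days after the nominal visit.
- Reconcile the terms investigational product and study treatment in the follow-up-to-resolution sentence, so that it is clear which events it covers.

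The cost is the wording changes and one extra call for patients not yet on new therapy. Reported AE rates may rise slightly. Patients already past the 30-day visit when the change takes effect will have the shorter window, which the study report should state.

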10.2.5.4 Rapid Notification of Adverse Events of Interest

In addition to serious adverse events, the following adverse events will be reported within 24 hours using the same rapid notification procedures that are used for serious adverse events, even if the nature of the adverse event is not deemed serious:

- Any overdose (defined as the accidental or intentional administration of any dose of a product that is considered both excessive and medically important).
- Any suspected transmission of an infectious agent via study treatment. An infectious agent is defined as any organism, virus, or infectious particle, pathogenic or nonpathogenic.
- Potential Drug-induced liver injury (DILI), defined as:
 - Alanine aminotransferase (ALT) or aspartate aminotransferase (AST) elevation > 3 times upper limit of normal (ULN)

AND

 - Total bilirubin > 2 times ULN, without initial findings of cholestasis (elevated serum alkaline phosphatase),

AND

 - No other immediately apparent possible causes of AT elevation and hyperbilirubinemia, including, but not limited to, viral hepatitis, pre-existing chronic or acute liver disease, or the administration of other drug(s) known to be hepatotoxic.

- Death due to disease progression occurring within 28 days of study treatment; however, these events should not be documented as AEs or SAEs. If there is any uncertainty about the cause of death, the event should be reported as a serious adverse event.
- If a female becomes, or is found to be, pregnant within 6 months of exposure to the study treatments (maternal exposure) or if a male has been exposed to the study treatments within 6 months prior to contraception (paternal exposure).
- Any follow-up to the above-referenced events, including outcome of pregnancy. Further follow-up of birth outcomes will be handled on a case-by-case basis. In the case of paternal exposure, the investigator must obtain permission from the patient's partner in order to conduct any follow-up or collect any information.

